7.2 Termination of Study

This study may be terminated for safety concerns of the PI, CDC, or participating IRBs.

8 Statistical Analytic Plan

This study aims to enroll approximately 50 participants (~20 from Vanderbilt, ~20 from Cincinnati and ~10 from Duke). Since sample-sizes were predetermined and since this is a feasibility study, no power calculations were conducted. All analyses will be performed using R 3.2.3 (r-project.org), SAS version 9.4, or STATA version 14.

Feasibility Analysis

The proportion of children meeting the outlined feasibility benchmarks (Appendix, Table A1) will be determined.

Descriptive Statistics

Descriptive analyses will be summarized for continuous variables with mean, standard deviation, median, and interquartile range. Categorical variables will be summarized with frequencies and percentages. Explanatory figures will be generated to evaluate the data distribution. Comparisons of demographic characteristics between cclIV4 and IIV4 groups will be conducted using Pearson Chi-square and Wilcoxon tests appropriately.

Primary Objective

To assess the feasibility of conducting a randomized prospective safety study of LAIV4 versus IIV4 during the 42 days after vaccination in children aged 5-11 years with persistent asthma of varied severity (cclIV4 will be used as a surrogate for LAIV4)

Primary Outcomes Measures

1. Assess the proportions of those achieving Feasibility Benchmarks (Table A1 Appendix)
2. Qualitatively describe best practices and lessons learned

Secondary Objectives

1. To compare proportions of local and systemic reactogenicity events during the 14 days after cclIV4 versus IIV4 in children with asthma aged 5-11 years.
2. To describe the unsolicited and serious adverse events in children receiving cclIV4 and IIV4 during the 42 days.
3. To compare proportions of asthma exacerbations during the 14 days after cclIV4 versus IIV4 in children with asthma aged 5-11 years.
4. To compare proportions of asthma exacerbations during the 42 days after cclIV4 versus IIV4 in children with asthma aged 5-11 years.
5. To explore differences between the cclIV4 and IIV4 groups regarding clinical asthma symptoms after vaccination and changes in asthma control before and after vaccination in children with asthma of varied levels of severity.

Secondary outcome measures

1. Proportion of subjects with solicited local and systemic reactogenicity events for 14 days after vaccination between recipients of cclIV4 and IIV4.
2. The nature and frequency of the unsolicited and serious adverse events will be described in children receiving cclIV4 and IIV4 during the 42 days.
3. Proportions of asthma exacerbations in recipients of cclIV4 and IIV4 during the 14 days post-vaccination (until day 15). The asthma exacerbation proportion within 14 days post-vaccination will be calculated for children receiving cclIV4 or IIV4 influenza vaccine. For this calculation a child with an asthma exacerbation (as defined earlier in the protocol) on one or more days during day 1-15 would be considered to have had an asthma exacerbation (dichotomous yes or no). We will compare proportions in children receiving cclIV4 vs. IIV4.
4. Proportions of asthma exacerbations in recipients of cclIV4 and IIV4 during the 42 days post-vaccination (until day 43). The asthma exacerbation proportion within 42 days post-vaccination will be calculated for children receiving cclIV4 or IIV4 influenza vaccine. For this calculation a child with an asthma exacerbation (as defined earlier in the protocol) on one or more days during day 1-43 would be considered to have had an asthma exacerbation (dichotomous yes or no). We will compare proportions in children receiving cclIV4 vs. IIV4.
5. Proportions of clinical symptoms after vaccination and changes in measurement of asthma control, before and after vaccination in children with asthma of varied levels of severity, between recipients of cclIV4 or IIV4 will be assessed through five measures (see methods for schedule):
 - A. Proportions of subjects with asthma symptoms as assessed on memory aid (e.g., wheezing, nighttime awakenings, cough) during days 1 through 15.

Proportions of subjects with each asthma symptom (dichotomous yes or no) by treatment group, and asthma severity level will be calculated and a 95% confidence interval of the difference in proportions between the treatment groups will also be presented.
 - B. Change in Peak Expiratory Flow Rate (PEFR) after vaccination from baseline (pre-vaccination) PEFR.

Peak Expiratory Flow Rate (PEFR) evaluations are recorded once every day starting on day 1 (baseline) through day 15; PEFR measurement will also be performed on day 43. Proportion of subjects with clinically important change of $\geq 20\%$ decrease in PEFR (dichotomous yes or no) will be calculated at baseline (day 1), during days 2 through 15 (observed $\geq 20\%$ decrease on one or more days) and on day 43. Comparisons of proportions between days 2 through 15 or day 43 with baseline will be conducted between the two treatment groups and 95% CIs of such proportion differences will be presented. Comparisons of mean/median between each day after vaccination with baseline will also be conducted between the two treatment groups and 95% CIs of such differences will be presented.

Each subject will have repeated PEFR measurements (baseline, once a day for days 1-15 and once on the last study day 43), which naturally provides a longitudinal data set. We plan to explore the change in PEFR after vaccination for up to 43 days between cclIV4 and IIV4 groups through a full likelihood longitudinal analysis such as a mixed effects model. We may adjust for covariates listed below while accommodating multiple random subject effects. We may apply restricted cubic splines for some continuous covariates to relax the linearity

assumption. Estimates of average treatment effects along with 95% CIs will be reported for day 15 and day 43.

C. Change in Childhood Asthma Control Test (cACT) scores after vaccination from baseline (pre-vaccination) cACT

The cACT scores are recorded at baseline, days 4, 8, 15 and 43; lower scores indicate poorer asthma control for the interval. Proportions of subjects with cACT scores <20 (dichotomous yes or no) will be calculated at baseline (day 1), on days 4, 8, 15, and 43. Comparisons of proportions between days 4, 8, 15 or day 43 with baseline will be conducted between the two treatment groups and 95% CIs of such proportion differences will be presented. Comparisons of mean/median between day 4, 8, 15, or 43 with baseline will also be conducted between the two treatment groups and 95% CIs of such differences will be presented.

Similar full likelihood longitudinal analysis (stated in 8.2.4, 2, B) may be conducted using cACT measurements as the outcome.

D. Change in Pediatric Respiratory Outcome PROSE after vaccination from baseline (pre-vaccination) PROSE

The PROSE score are recorded at baseline, days 4, 8, 15 and 43. Comparisons of mean/median between day 4, 8, 15, or 43 with baseline will be conducted between the two treatment groups and 95% CIs of such differences will be presented.

Similar full likelihood longitudinal analysis (stated in 8.2.4, 2, B) may be conducted using PROSE measurements as the outcome.

E. Rates of medical utilization for asthma-related symptoms in recipients of cclIV4 and IIV4 during the 42 days post-vaccination (until day 43).

The rate of medical utilization for asthma-related symptoms is defined as the number of unscheduled medical visits divided by the length of follow-up time in days. We will report rate differences between the two treatment groups at day 15 and day 43 along with 95% CIs.

Covariates of interest are based on previous studies and epidemiological plausibility. The covariates listed below are for model consideration though they are not limited.

Main exposure: treatment group

Baseline measurement: PEFr, cACT, PROSE, asthma severity level such as severity status (mild, moderate or severe), control status (well-controlled or not well-controlled), and age, gender, race, daytime and nighttime asthma scores, nighttime awakening, BMI/BMI percentile

Other covariates may include days from immunization, community pollen levels near to the time of cclIV4 or IIV4 vaccination, exposure to second-hand smoke, and the frequency of smog alert/ozon alert days over the study interval in the communities where the children reside.

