3 ELIGIBILITY CRITERIA

3.1 Inclusion Criteria

1. Children between 5-11 years of age, inclusive, at enrollment

2. Participant must have a current diagnosis of persistent asthma¹

¹ *Physician diagnosis of asthma and current prescribed use of a daily controller medication*

3. Parent/legal guardian must provide written informed consent and subject must provide assent as appropriate for age prior to initiation of study procedures and according to local IRB requirement

4. Parent/legal guardian and subject must be willing and able to comply with planned study procedures and be available for all study visits

5. Children aged 5-8 years must have received at least 2 doses of seasonal trivalent or quadrivalent influenza vaccine prior to the current influenza season. Children 9-11 years must have received at least 1 dose of seasonal trivalent or quadrivalent influenza vaccine prior to the current influenza season.²

² *Influenza vaccination history verification Figure 2 appendix*

6. Is in good health, other than their asthma, as determined by medical history and targeted physical examination based on medical history

7. English or Spanish literate³

³ *only English speaking participants will be included at the Cincinnati site*

8. Intention of being available for entire study period and complete all relevant study procedures, including follow-up phone calls and collection of information

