3.3 Characterizing Asthma Severity

Prior to vaccination, it will be necessary to characterize asthma severity and control in each patient (see figures A1 through A3 in the appendix). This characterization will be based on the chart from the National Asthma Education and Prevention Program Expert Panel Report 3 that was issued in October 2007.¹⁷ For the purposes of the study, we will only recruit subjects with persistent asthma and within the full spectrum of severity. Subjects in well-controlled and not well-controlled categories will be enrolled; subjects with very poorly controlled asthma will be discussed with the physician prior to enrollment for their assessment as to whether these subjects can be safely enrolled, based on clinical judgment.

Table 1. Classification of Asthma Severity¹⁷

Lowest level of treatment required to maintain control	Classification of Asthma Severity			
	Treatment of Asthma			
	Intermittent	Mild Persistent	Moderate Persistent	Severe Persistent
Treatment Steps (includes prn SABA use)	Step 1	Step 2 Low dose ICS	Step 3 or 4 Low to Medium dose ICS AND/OR LABA or Montelukast	Step 5 or 6 High dose ICS AND/OR LABA or Montelukast
Additional considerations		Immunotherapy	Immunotherapy plus Asthma specialist	

Abbreviations: SABA: short-acting beta-agonist; LABA: long-acting beta-agonist; ICS inhaled corticosteroids

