4.9 Monitoring Vaccine Safety in the First 15 Days

On the vaccination day and for the next 14 days post-vaccination, all subjects will be monitored daily by their parents and the information will be recorded using memory aids provided at the enrollment visit. Daily reactogenicity, including measurement of nighttime awakening, and two asthma scoring systems will be completed (cACT score and the PROSE score).

In addition to the two symptom scores above, several predefined events that could occur after vaccine administration will also be recorded for 14 days after vaccination. These will include; fever (oral temperature $\geq 100.4^{\circ}\text{F}$), runny nose/ nasal congestion, sore throat, cough, wheeze, vomiting, change in activity level, appetite change, irritability, abdominal pain/stomachache, headache, chills, and muscle aches. Local reactions after the intramuscular vaccination will also be captured and include: redness, swelling, and/or pain around the injection site. Medication receipt, new prescriptions for asthma medications, and any previously unscheduled healthcare utilization (medical office visits, ED visits, hospitalizations) will also be documented on the reaction form. To ensure compliance with the reaction assessment, parents will be called or emailed through REDCap on Days 4, 8 and 15 by the study staff.

On the day of vaccination and during the first 14 days after vaccination, if the subject reports an increase in their symptoms and an increase in the need for medications for their asthma, the family will be instructed to contact the study staff, so medical records can later be collected, if applicable. If at any point a study participant is experiencing symptoms of any asthma exacerbation, the participant or their parent will be instructed to contact their PCP and inform study staff of this encounter.

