APPENDIX

[figure not shown]
Figure A1. Asthma Control Chart for Children 5-11 years of age¹⁷

Asthma Control Chart

FIGURE 3-5b. ASSESSING ASTHMA CONTROL IN CHILDREN 5–11 YEARS OF AGE

Components of Control		Classification of Asthma Control (Children 5–11 years of age)		
		Well Controlled ≤2 days/week but not more than once on each day	Not Well Controlled >2 days/week or multiple times on ≤2 days/week	Very Poorly Controlled Throughout the day
Impairment	Symptoms			
	Nighttime awakenings	≤1x/month	≥2x/month	≥2x/week
	Interference with normal activity	None	Some limitation	Extremely limited
	Short-acting beta ₂ -agonist use for symptom control (not prevention of EIB)	≤2 days/week	>2 days/week	Several times per day
	Lung function • FEV ₁ or peak flow • FEV ₁ /FVC	>80% predicted/ personal best >80%	60–80% predicted/ personal best 75–80%	<60% predicted/ personal best <75%
Risk	Exacerbations requiring oral systemic corticosteroids	0–1/year	≥2/year (see note)	
	Consider severity and interval since last exacerbation			
	Reduction in lung growth	Evaluation requires long-term followup.		
	Treatment-related adverse effects	Medication side effects can vary in intensity from none to very troublesome and worrisome. The level of intensity does not correlate to specific levels of control but should be considered in the overall assessment of risk.		

Key: EIB, exercise-induced bronchospasm; FEV₁, forced expiratory volume in 1 second; FVC, forced vital capacity; ICU, intensive care unit

Figure A2. Daily Medication Steps for Persistent Asthma¹⁷

Key: Alphabetical order is used when more than one treatment option is listed within either preferred or alternative therapy. ICS, inhaled corticosteroid; LABA, inhaled long-acting beta₂-agonist, LTRA, leukotriene receptor antagonist; SABA, inhaled short-acting beta₂-agonist

Notes:

- The stepwise approach is meant to assist, not replace, the clinical decisionmaking required to meet individual patient needs.
- If alternative treatment is used and response is inadequate, discontinue it and use the preferred treatment before stepping up.
- Theophylline is a less desirable alternative due to the need to monitor serum concentration levels.

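### Outcome 5A reduces each daily symptom record to one yes/no over 15 days, which discards frequency and responds poorly to worsening in children who have a symptom on about two or more days a week

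*Combined protocol and SAP*

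**What the plan says.** Section 8 defines 5A as "Proportions of subjects with asthma symptoms as assessed on memory aid (e.g., wheezing, nighttime awakenings, cough) during days 1 through 15". The scoring is "Proportions of subjects with each asthma symptom (dichotomous yes or no) by treatment group, and asthma severity level will be calculated". The arms are then compared by the difference in these proportions, reported with a 95% interval. No symptom-day count, intensity or baseline term is given.

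The text does not say how 15 daily entries become one yes or no. The 14-day exacerbation outcome does: a child with an event "on one or more days during day 1-15 would be considered to have had an asthma exacerbation". The PEFR outcome (5B) also uses a one-or-more-days rule, with Day 1 as baseline and Days 2-15 as follow-up. Any day in Days 1-15 is therefore the natural reading of 5A, but it is an inference.

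On the population, Section 3.1 defines persistent asthma as "Physician diagnosis of asthma and current prescribed use of a daily controller medication", with no symptom-frequency requirement. Section 3.3 states: "Subjects in well-controlled and not well-controlled categories will be enrolled". Very poorly controlled children may enter after discussion with the physician. In Figure A1, well-controlled children have symptoms on at most 2 days a week and wake at night at most once a month. The not-well-controlled symptom entry is ">2 days/week or multiple times on ≤2 days/week", with awakenings at least twice a month.

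Section 8 gives no expected symptom prevalence, no expected mix of control status and no power calculation.

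**The concern.** Parents record symptoms every day, but 5A keeps one bit per symptom per child. A child with 3 cough days and a child with 15 score the same. Where a symptom is already common before vaccination, most children will be a yes in both arms whatever the vaccine does. A real rise in symptom days could then appear as no difference.

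The study exists to prepare a later LAIV4 safety trial in the same population. As written, 5A would give that trial a yes/no prevalence for each symptom, but no mean or variance of symptom days unless someone goes back to the daily records.

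**Working it through.** The plan states no rate, effect size or power for 5A, so there is no figure to reproduce. The check asks how an any-day score behaves across plausible symptom rates.

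**Inputs from the documents.** 15 diary days; about 50 children randomised 1:1, so about 25 per arm; the Figure A1 limits above.

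**Assumptions.** The symptom rate for a single symptom, the correlation of days within a child, and a doubling of the daily rate as the effect. Figure A1 gives one overall symptom frequency; the rate for wheeze alone or cough alone can only be equal or lower.

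**Step 1. Chance of a yes with independent days.** For r symptom days a week, P(any) = 1 − (1 − r/7)^15, and mean symptom days = 15r/7.

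| r (days/week) | P(any) | Mean days |
|---|---|---|
| 0.5 | 67% | 1.1 |
| 1 | 90% | 2.1 |
| 2 | 99.4% | 4.3 |
| 4 | about 100% | 8.6 |

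At r = 2: 1 − (5/7)^15 = 0.994. Doubling from 2 to 4 moves the endpoint by 0.6 points.

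**Step 2. Nighttime awakenings.** For m per 30 days, P(any) = 1 − (1 − m/30)^15. This gives 40% at m = 1, 64% at m = 2 and 88% at m = 4. There is no ceiling at the well-controlled limit, nor at the lower edge of the not-well-controlled range.

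**Step 3. Relaxing independence.** If symptoms come in episodes averaging 3 days (two-state Markov chain), P(any) is 61% at 1 day a week, 90% at 2 and about 100% at 4. If children differ in their underlying rate (beta-binomial, intraclass correlation 0.3), P(any) is 31%, 53%, 80% and 92% at 0.5, 1, 2 and 3 days a week. Doubling then adds 17 points at 2 days a week (80% to 97%) and 22 points at 0.5 (31% to 53%).

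**Step 4. What a day count would add.** Simulated power at 25 per arm for a doubled rate, two-sided 5%: Pearson chi-square on any/none against Wilcoxon on symptom days.

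| Baseline rate | Independent days: any/none vs count | Correlation 0.2: any/none vs count |
|---|---|---|
| Awakenings, 1/month | 48% vs 54% | 27% vs 26% |
| 0.5 day/week | 57% vs 87% | 47% vs 45% |
| 1 day/week | 20% vs >99% | 55% vs 73% |
| 2 days/week | 0% vs 100% | 34% vs 98% |

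With correlation 0.3 at 2 days a week, the figures are 54% and 93%.

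**Step 5. A mixed population.** Suppose half the children have 0-2 symptom days a week and half 2-5, in 2-day episodes. Nominally doubling every rate moves any/none from 83% to 91%. The well-controlled half moves from 66% to 83%; the other half from 99.7% to 100%. Mean days rise from 4.8 to 7.1, a factor of about 1.5 rather than 2, because 2-day episodes cap how frequent symptoms can become in this model. Power at 25 per arm is about 15% for any/none and about 60% for the count.

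**Step 6. Dependence on diary completion.** Table A1 accepts 11 of 15 diary days. At 1 day a week with independent days, P(any) is 90% over 15 entries and 1 − (6/7)^11 = 82% over 11. The score shifts with completeness, and 5A gives no denominator rule.

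**The case against.** A reader might infer that 5A sits at its ceiling throughout and cannot show worsening. The documents do not support that. Eligibility rests on diagnosis and controller use, so children with few or no symptoms can enrol. The not-well-controlled entry in Figure A1 also admits children with symptoms on 2 or fewer days a week. Awakenings, one of the three named symptoms, do not saturate at one or two a month, and in Step 5 the well-controlled half still moves by 17 points. All of this stands.

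A reader might also infer that change from baseline goes unmeasured. Objective 5 has two parts: symptoms after vaccination, and change in asthma control. 5A serves the first; 5B, 5C and 5D serve the second, each with a baseline. Randomisation stratified by severity allows an arm comparison without a pre-vaccination diary. Nor is 5A the only use of the daily record: the solicited events in Section 4.9 include "runny nose/ nasal congestion, sore throat, cough, wheeze, vomiting, change in activity level, appetite change", which feed outcome 1.

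A third tempting inference is that a Day 1 awakening must refer to the night before vaccination, since Table A1 says this item is done in the morning. The memory aid itself is not among the documents, so this cannot be confirmed.

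Finally, 5A is one of several exploratory measures in a study of about 50 children. At 25 per arm the half-width of the 95% interval is 1.96 × √(2p(1−p)/25), or 25 to 28 points for p between 30% and 70%. Precision limits 5A even where there is no ceiling. That also stands and lowers the priority. It does not answer the loss of frequency information, which costs little to repair.

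**Conclusion.** The point holds in a limited form. Scored as any day, 5A discards frequency and is insensitive to worsening in children who have a given symptom on about 2 or more days a week, a range that Figure A1 places in the not-well-controlled category the trial enrols. At 2 days a week a doubling moves the endpoint by 0.6 points (independent days) to 17 points (correlation 0.3). For infrequent symptoms, and for many well-controlled children, the yes/no score works about as well as a count.

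The size rests on assumed symptom rates, correlation structure, control mix and effect, and the any-day rule is itself inferred. Given the exploratory status of 5A, the level is consider.

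**What to change.** In Section 8, 5A:

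- State the scoring rule: yes if the symptom is recorded on one or more days in the window. Keep the yes/no proportion and its interval.
- Add, for each symptom, the number of symptom days divided by the number of days with a diary entry over Days 2-15, the PEFR follow-up window in 5B. Report the difference between arms in the mean of this proportion with a 95% confidence interval, by severity stratum.
- Optionally adjust for baseline measures already collected or listed as covariates, such as control status, PROSE or nighttime awakening.

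The cost is one derived variable and a few sentences of SAP text, with no new visits, forms or participants. The added measure needs a rule for missing diary days, for example a minimum number of entries, and brings little for rare symptoms.

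### The committed PEFR, cACT and PROSE mean comparisons (Section 8, 5B-5D) are specified without a baseline covariate, a severity term or a site term, which gives away some precision in a trial of about 50 children

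*Combined protocol and SAP*

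**What the plan says.** **Design.** Section 4.2 randomizes 1:1, separately at each of three sites, stratified by severity (mild vs moderate/severe). Section 4.3.1 collects PEFR, cACT and PROSE on every child at Visit 1, before vaccination.

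**Committed comparisons (Section 8).**
- 5B, PEFR: "Comparisons of mean/median between each day after vaccination with baseline will also be conducted between the two treatment groups".
- 5C, cACT: "Comparisons of mean/median between day 4, 8, 15, or 43 with baseline will also be conducted between the two treatment groups".
- 5D, PROSE: "Comparisons of mean/median between day 4, 8, 15, or 43 with baseline will be conducted between the two treatment groups".

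Each comes with 95% CIs. None names a test, a model, a covariate or a stratification term.

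**Longitudinal models.** For PEFR a mixed model is planned, and the plan undertakes to report its results: "Estimates of average treatment effects along with 95% CIs will be reported for day 15 and day 43". Its adjustment is optional: "We may adjust for covariates listed below while accommodating multiple random subject effects". For cACT and PROSE the model itself is optional: "Similar full likelihood longitudinal analysis (stated in 8.2.4, 2, B) may be conducted using cACT measurements as the outcome", and for PROSE a similar analysis "may be conducted using PROSE measurements as the outcome".

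**Covariate list.** It is introduced with "The covariates listed below are for model consideration though they are not limited". It includes baseline PEFR, cACT and PROSE and the severity level. Site is not on it and is not named in any other analysis.

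**The concern.** A change score does use baseline, but it fixes the baseline slope at 1. Unless baseline and follow-up are very highly correlated, estimating the slope gives a smaller variance from the same data. A change score also carries part of any chance baseline difference between arms into that trial's estimate. Site and severity were judged important enough to define the randomization, but no committed comparison uses them.

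For cACT and PROSE, the simple comparison may be the only between-arm result for means, because the model that could adjust need not be run. For PEFR, the reported day 15 and day 43 estimates depend on covariates chosen later from an open list. At stake is the width of the reported intervals, and some analyst discretion, in a small trial.

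**Working it through.** **Inputs from the documents.** N is about 50 (20 + 20 + 10 = 50 by site), so n = 25 per arm. CIs are 95%. The response benchmarks in Table A1 are 80% for the day 4, 8 and 15 calls and 70% for the day 44 call. Section 8 states that no power calculation was done, and no SD or correlation is given, so there is no planned figure to reproduce.

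**Assumed.** Equal SDs, and a baseline/follow-up correlation r from 0.3 to 0.9. Results are in SD units and apply to means, not medians.

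**Step 1: baseline covariate.**
- Change score: SE = sqrt(2(1-r) × 2/n), with t on N-2 df.
- ANCOVA on baseline: SE = sqrt((1-r²) × 2/n × (1+1/(N-4))), with t on N-3 df.
- At r = 0.5: change 2.011 × sqrt(1 × 0.08) = 0.569; ANCOVA 2.012 × sqrt(0.75 × 0.08 × 47/46) = 0.498.

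| r | Change, half-width | ANCOVA, half-width | Change wider by |
|---|---|---|---|
| 0.3 | 0.673 | 0.549 | 23% |
| 0.5 | 0.569 | 0.498 | 14% |
| 0.7 | 0.441 | 0.411 | 7% |
| 0.8 | 0.360 | 0.345 | 4% |
| 0.9 | 0.254 | 0.251 | 1.4% |

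At the response benchmarks and r = 0.5, the half-widths are 0.640 vs 0.563 with 40 children and 0.688 vs 0.606 with 35. Both change-score intervals are about 14% wider.

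**Step 2: chance baseline difference.** With SE sqrt(2/25) = 0.283, the probability that the arms differ by more than 0.3 SD at baseline is 29%. It is 24% if site and severity explain an assumed 20% of baseline variance. Compared with ANCOVA, a 0.3 SD difference moves the change-score estimate by (1-r) × 0.3: 0.15 SD at r = 0.5 and 0.06 SD at r = 0.8. Both are well inside the half-widths above.

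**Step 3: site and severity.**
- If they explain an assumed 10% or 20% of the residual variance after baseline adjustment, omitting them from ANCOVA widens the interval by 1/sqrt(0.9) = 1.05 or 1/sqrt(0.8) = 1.12.
- If their effect is the same at baseline and follow-up, it cancels in a change score, so omitting them there costs nothing. In ANCOVA, suppose they explain a share p of total variance at both times and r = 0.5 overall. The residual variance with strata is (1-p) × (1-((0.5-p)/(1-p))²), against 0.75 without. At p = 0.1 it is 0.722, ratio sqrt(0.75/0.722) = 1.02. At p = 0.2 it is 0.6875, ratio 1.04. Allowing for the degrees of freedom, the gain from including them is about 1.5% to 4%.
- If they explain nothing, including them costs about 0.5% (in simulation at r = 0.3, half-width 0.546 to 0.549).

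**Step 4: PEFR mixed model.** Take baseline on day 1 plus 15 follow-ups (days 2-15 and 43), compound symmetry, r = 0.5 and 25 per arm.
- Categorical visits with arm-by-visit means and a free baseline mean in each arm: day 43 SE = sqrt(2 × 0.5 × 0.08) = 0.283, the change-score value.
- The same with a common baseline mean: sqrt(0.75 × 0.08) = 0.245.
- Linear time in each arm: the sum of squares of the 16 days about their mean is 1428.4, so the SE of the slope difference is sqrt(0.5 × 0.08/1428.4) = 0.00529. That gives 14 × 0.00529 = 0.074 for change to day 15 and 42 × 0.00529 = 0.222 for change to day 43.

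So the precision of the mixed model depends on how baseline and time enter, and the plan leaves both open.

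**The case against.** The strongest reply has four parts.

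1. **Baseline is not ignored.** Outcomes 5B-5D are defined as changes from baseline, and the covariate list contains the baseline scores and severity. This stands. What is missing is a committed baseline covariate and any mention of site.

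2. **A change score is valid under randomization and answers the stated question.** This also stands. A reader might infer biased estimates or inflated type I error, but the documents support neither. Allocation is random. Omitting prognostic strata leaves intervals correct or conservative. In simulations with strata explaining 0% to 20% of residual variance, the baseline-only model covered 94% to 97.5%.

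3. **The mixed model may already do the job.** A reader might infer the opposite, that it is bound to reproduce the change score. That holds only with categorical visits, arm-by-visit means and a free baseline mean in each arm. The plan lists days from immunization as a covariate and allows splines for continuous covariates. A smooth time curve behaves differently, as step 4 shows, though its precision depends on the curve being right. This defence does not reach cACT and PROSE, where no model is promised.

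4. **The stakes are small.** Objective 5 is exploratory, no power is claimed, and the gain nearly vanishes at high r. It is also tempting to say that leaving out site and severity always makes intervals too wide. It does not for a change score when their effect is stable over time. This limits the size of the point but does not remove it, because the improvement is free.

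**Conclusion.** The concern holds in a limited form and is minor. The committed mean comparisons are most naturally read as unadjusted change scores, and for cACT and PROSE they may be the only ones reported. The cost is precision: intervals from 1.4% to 23% wider than baseline-adjusted ones for r between 0.9 and 0.3. Site and severity add a gain of about 5% or 12% if they explain 10% or 20% of the residual variance, and about 1.5% to 4% if their effect is stable over time. Including them costs about 0.5% if they have no effect.

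These sizes rest on assumed correlations and stratum effects, equal SDs and about 25 children per arm. Only the sample size, the confidence level, the response benchmarks and the allocation scheme come from the documents. The concern about choosing covariates after seeing the data applies to the optional adjustment in the models, not to the simple comparisons. The feasibility benchmarks are unaffected.

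**What to change.** In Section 8, 5B-5D, add after each mean/median sentence:

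> *Between-arm mean comparisons will be estimated by ANCOVA of the follow-up value on arm, the child's own baseline value, site, and severity as randomized (mild vs moderate/severe).*

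In 5B, replace the optional adjustment with:

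> *The PEFR mixed model, and any cACT or PROSE mixed model, will include the same baseline, site and severity terms.*

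If baseline is a covariate in a mixed model, it should not also be one of the responses. State whether time enters as categorical visits or as a curve. Keep unadjusted changes and medians as descriptive results, and the other listed covariates as exploratory.

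The cost is SAP wording and about four degrees of freedom per comparison (baseline 1, site 2, severity 1). No new data are needed.
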